In most cases, participants who are recruited on-site at a CDPH clinic will have already completed STI testing as a part of their clinic visit. CDPH clinics also test for STIs using the FDA approved APTIMA assay. Participants who have already completed STI testing will be asked to consent to the clinic's UIC lab sharing their results with study staff via fax. KIU! staff will call the lab client services and provide the patient name, date of birth, and date of specimen collection in order to verify that correct results are sent. In addition, KIU! staff will verify the fax number to which the results should be sent. The fax machine to which results will be sent is located in the mail room of Northwestern's Department of Medical Social Sciences (MSS). The MMS office is not open to the general public. The office is only accessible to staff with ID cards and invited guests who are buzzed into the office. Guests are typically escorted through the office by staff. In general, only MSS staff access the fax machine. To protect participant's confidentiality, KIU! staff will ask the lab to confirm the time that the fax will be sent so that the results are immediately retrieved from the fax machine. All faxes of results will also include a fax cover sheet that describes the confidential nature of the contents and has instructions to notify the sender to report any faxes received in error and destroy the misdirected documents. The cover letter also warns that any mishandling of the documents, such as copying or dissemination, is illegal. It typically takes 3 – 7 days for the return of results. CDPH staff will be responsible for providing these participants with treatment and reporting positive results to appropriate authorities. During instances in which a client has not already completed STI testing or declines to consent to the clinic's UIC lab sharing their test results, university staff will offer the client the option to take the test kits home, be mailed the test kits by university staff, or selfadminister the test kits while still on-site at the CDPH clinic. Participants who self-administer at home will be responsible for mailing the kits back to the CDC for analysis. Participants who self-administer on-site at the CDPH clinic will have their kits mailed by university staff to the CDC for analysis.

All STI results will be manually entered into the study's REDCap tracking database. In order to avoid data entry errors and sharing incorrect results with participants, the study team will do comprehensive checks on logged results and the PDFs of results sent to participants (see "C.2.d. Protection against a Breach of Confidentiality" for more details).

If a participant's specimen is positive, the Physician of Record at the CDC reviews the results before releasing to participants. We will deliver test results to participants using a secure, encrypted email. To open the email and access their results, participants must enter the study ID that was provided to them with their test kit. They will be able to download and print out a hard copy of their results. Participants may speak to research staff if they wish. With positive test results for chlamydia or gonorrhea, research study staff will: (1) encourage participants to notify current and past sex partners; (2) provide local referrals for free or low cost treatment; and (3) make a legally required confidential report to the appropriate health department. Health department professionals (or disease information specialists) may contact and interview the participant to obtain names of his sex partners to notify and encourage them to seek evaluation and treatment. STI testing and results will also be self-reported at behavioral assessment time points throughout the follow-up period to determine if a participant tested positive and was treated prior to the 12-month STI test.

**B.11. RCT Analytic Plan.** This is a two-group, active-control, RCT of an online intervention. The study's hypothesis concerns between-group differences in the change in HIV/STI risk behavior and STI incidence from pre-intervention to later follow-ups. There are 4 assessment points of RCT outcomes: baseline, 3, 6, and 12 months post-intervention. Prior to conducting full analyses, standard descriptive analyses will be conducted to check for invalid values, outliers, and logical consistency between variables. We will assess the comparability of the experimental and control groups at baseline. If any variables differ significantly at baseline, they will be included as covariates in the adjusted outcome analyses along with variables known from prior research (e.g. age) to be correlated with the outcome under analysis. Following extensive data description and analysis at separate follow-up points, the primary analysis will utilize all follow-up points by fitting mixed effect regression models. Also known as hierarchical linear models (HLM) , these models allow for the presence of missing data, time-varying or invariant covariates, and subject measurement at different time points. HLM models appropriate to the characteristics of the distribution (i.e. normal, Poisson) will be fit using SAS.

The primary behavioral outcome measure of treatment success will be the count of unprotected anal sex acts and the biomedical endpoint will be NG/CT incidence (Aim 2). Secondary outcomes include: condom errors, IMB factors, and receipt of an HIV test. We will also explore intervention effects separately for receptive and insertive anal sex. The primary independent variable of interest is the indicator for the intervention group. The baseline value of the outcome and other required covariates at baseline will be included as additional independent variables. The intervention will recruit participants from multiple sites (multiple clinics in three cities); however it is not delivered in groups so site will be adjusted for as a fixed rather than a random independent variable. A random intercept term will be included to account for individual average levels of the outcome. The effect of time will first be estimated as a categorical variable in order to describe and adjust for time trends as observed. A second strategy will start with estimating a single slope reflecting average change across all 4 time points, then add a guadratic term if it contributes significantly to the model. Random effects for time variables, reflecting individual variations in time trends, will be included in addition to random intercepts, if significant. A single effect of group will test the intervention effect averaged across all time points, adjusting for all included covariates and underlying time trends. Potential moderators (race/ethnicity, relationships status, and gay/bisexual identity) will be added as independent variables and their interactions with intervention group will be tested (Aim 3). Addition of interaction terms between time and intervention group will provide a test for comparing time trends in change scores between groups.

Analysis of all available measurements among all participants regardless of dose is consistent with an "intent-to-treat" perspective. It is desirable to also perform an analysis which considers the "dose" and engagement in the intervention. We will use Rubin's causal modeling to consider dose-effect when making comparisons across the two groups. Further, in our HLM models, missing data is assumed to be missing at random conditional on the independent variables in the model; therefore we are in effect assuming that participants with incomplete measurements would have been similar to others in their group (their same covariate values) with complete measurements.

B.12. Power and Sample Size. All power calculations were performed in R version 2.14.0 and using common sample size formula for repeated measures with nominal Type I error rates (i.e.  $\alpha$ =.05) and effect estimates based on our preliminary studies. We will screen approximately 4500 YMSM, enroll 900 YMSM, and assume 80% retention based on our preliminary studies. Assuming participants are randomized to two groups in equal proportions, we will have 97% power to detect a 11% reduction in the rate of unprotected sex (ERR = 0.89) due to the intervention, assuming the correlation between repeated measures is 0.8. The correlation among repeated measures plays an important role in the calculation; in this case, our power calculation is conservative if the correlation among repeated measures is, in fact, weaker than 0.8. The smallest effect size with which we will have 80% power to detect is a 6.5% reduction in the rate of unprotected sex. Technically speaking, our study will have greater power than what is reported here after we adjust for our blocked design. In conclusion, we will have 80% power to detect an effect size equal to half of what we observed in our pilot trial and less than half of the lower bound of effect sizes seen in other HIV prevention programs with MSM. For our primary biomedical endpoint of STI incidence, we assume the annual incidence based on our longitudinal cohort studies in the range of 10 to 15%. If the incidence rate in the control group is 10%, we will have 81%, 70%, and 56% power to detect an incidence reduction of 7%, 6%, and 5%, respectively. If the incidence rate in the control group is higher, say 15%, then the power reduces to 71%, 60%, and 47%, respectively. The objective of aim 3 is to estimate the intervention effect among subgroups and test for significant differences. In data analyses, this will be achieved by testing 2-way interactions, treatment by subgroup. For a conservative power calculation, we repeated the power calculations as per aim 1 with a reduced sample size. Assuming N=200 per group (say, for racial/ethnic subgroups), an ERR=0.89 as above, and strong correlation among repeated measures (i.e. 0.8), we will have 91%, 85%, and 77% power to detect a 10%, 9%, and 8% reduction in the rate of unprotected sex among YMSM, respectively, due to KIU! intervention. The power will be less for effect sizes more subtle than 8% and less for smaller subgroups. In addition to racial/ethnic subgroups, other subgroups of interest include sexual orientation identity groups (81% gay, 17% bisexual identified) and relationship groupings (30% recent serious relationships). The power for each subgroup comparison will be similar to the power described above.

**B.13.** There are several alternatives to the design proposed here that deserve consideration. First, is the linkage of the online intervention to HIV testing, instead of recruiting YMSM online (e.g. banner ads). Online recruitment has been used extensively for other online HIV behavioral research projects with MSM, but with a few important exceptions these studies have had difficulties with recruitment of racial/ethnic minorities and with longitudinal retention. We believe that linking to HIV testing is an innovative method to help overcome these issues while simultaneously addressing the increasing lack of prevention counseling in this context. Furthermore, it advances the science of linking eHealth intervention into clinical encounters, which can then be applied to the inclusion of eHealth prevention in future biomedical prevention strategies (e.g. PrEP). Second, we considered using HIV status as a trial outcome. We ruled out this alternative for two reasons: a) by recruiting YMSM that just tested negative, seroconversions across one year would be a rare event and therefore require a cost prohibitive sample size (N > 4,500), and b) conducting HIV testing as part of the study would not allow us to include elective testing as a trial outcome.

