#### **PROCEDURES**

Participants will be recruited (1) from the HIV testing clinics and mobile testing units of our partner CBOs in Chicago, New York, and Atlanta, (2) from HIV testing at Hunter College and Emory University, (3) from athome HIV testing, (4) from street outreach efforts of university staff and interns, (5) using print, online, and

recorded ads, (6) by referral from ongoing studies and IRB-approved research participant registries at the university sites, (7) by referral from community partners who provide HIV testing, and (8) from Chicago Department of Public Health (CDPH) clinics. Eligible participants across all study sites will be offered the opportunity to visit Emory University, Hunter College, or Northwestern University to complete the baseline assessment and complete their first set of self-administered STI test kits. Regardless of recruitment source, prior to beginning the intervention, participants will still have the contact with an HIV testing counselor or study team member that is important for recruitment and retention. They will be randomly assigned into one of two study groups, either the KIU! intervention or an HIV knowledge control condition. They will be asked to complete online questionnaires (five questionnaires total, approximately 20 - 40 minutes each), complete an online intervention within 3 weeks, and maintain consistent online contact throughout the course of the study (a total of 12 months after enrolling). This research includes at-home urine tests and at-home self-administered rectal swabs for STIs. Both STI tests will be collected at pre- and post-intervention (12 month follow-up). Participants who test positive at baseline will be tested at 3 month and 6 month follow-up in addition to at the 12 month follow-up.

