- **B.6. Justification for STI incidence as a biological endpoint.** STIs are important risk factors in the transmission and acquisition of HIV infection due to increased biological susceptibility. Randomized trials suggest that STI control may have beneficial effects on HIV incidence in populations with high STI rates and growing HIV epidemics such as with YMSM (with limited effects in generalized epidemics). As such, there has been a call to incorporate STI testing and treatment into HIV prevention programs at the individual and community levels. At the same time, STI infections can serve as sensitive biomarkers in efficacy trials of sexual risk reduction interventions, particularly when HIV infection rates are too low to allow sufficient power with attainable sample sizes. In the current study, HIV incidence is not viable as a biomedical endpoint because participants are recruited upon receiving an HIV negative test result and, given the annual incidence of infections among tested MSM, a sample of >4,500 would be required to identify a moderate intervention effect, which would exceed budgetary allowances.

We propose to test for urethral and rectal Gonorrhea (NG) and Chlamydia (CT) and refer for treatment in both arms of the trial. Joint NG/CT incidence will serve as a biomedical endpoint for establishing intervention efficacy and as a means for determining the feasibility of incorporating an innovative approach to STI testing into an online HIV prevention solution. In addition to urethral NG/CT, we will test for rectal NG/CT because recent research has shown rectal infection to be just as common, if not more, than urethral infections. Study

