Similar procedures and measures successfully used in the developmental study will be employed. Assessments will be completed via the Internet using a Computer-Assisted Self Interview (CASI). We will administer knowledge/information based measures immediately post-intervention along with the measures of intervention acceptability and tolerability. Motivation, skills (i.e. partner sexual communication, correct condom use), and behavioral outcomes (i.e. number of insertive and receptive unprotected anal sex acts, condom errors) will be measured at all follow-up points. Whenever possible, we selected measures: (1) designed for high-risk YMSM to maximize sensitivity, (2) previously tested with diverse populations to minimize cultural bias, and (3) to maximize comparability to other studies in order to compare findings. All measures and a table depicting what is assessed at each time-point can be found in Appendix 2. Participants will be paid for completing assessment waves (~30 minute duration; See Budget Justification). As we have done successfully in prior online studies, participants will be given the option of receiving payment in person or via mail.

|                     | Construct                                       | Measure   |
|---------------------|---|---|
|                     | Administration Points                           |   |
| Primary
Outcomes | Unprotected sex acts and HIV testing  BL 3 6 12 | The AIDS-Risk Behavior Assessment (ARBA)  has been used with YMSM  and assesses behaviors on a partner-by-partner level, starting with recent partners, as well as in the aggregate. Partners are classified as serious or casual and relationship duration is measured  . Questions differentiate between insertive and receptive anal sex. The ARBA will also assess secondary outcomes of HIV testing behaviors. |
| P Q                 | STI incidence                                   | CT and GC testing of urine and rectal samples using the FDA cleared Gen-Probe APTIMA  |

|                    | BL 3 6 12   | Combo 2 Assay. All participants will be tested at baseline and 12 month follow-up. Participants who test positive at baseline will also be tested at 3 month and 6 month follow-ups.  |
|--------------------|---|---|

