(e) Exit Interviews: We have created a short exit interview script to collect qualitative data from participants after they complete their final 12 month follow-up assessment. We will conduct 20 exit interviews by phone to hear participants' thoughts on the intervention and its effect on their behavior. Ten participants will be randomly selected from a pool of intervention completers who responded well to the intervention (defined as a reduction in condomless anal sex acts at 12-month follow-up) and ten participants will be randomly selected from a pool of intervention completers who did not respond well to the intervention (defined as no change or an increase in condomless anal sex acts at 12-month follow-up). By including people who did versus did not respond well to the interview, we will be able to better understand differences in participants' experiences that may have contributed to whether or not the intervention changed their behavior. We will record the interviews by putting the call on speakerphone mode and using a handheld digital recording device. Before beginning the exit interviews, the study team will ask participants for verbal consent that they agree to complete the exit interview and have the conversation recorded. Participants will be reminded that all of the information they provide during the exit interview is confidential and that they can refuse to answer any questions that they do not feel comfortable answering. The study team will transcribe the audio and review responses for feedback on the intervention. The information gained from the qualitative interviews will be used to continue to refine the intervention in future iterations. It will also help the study team to understand whether or not participants find it acceptable to complete and return biological samples for STI testing, which will inform future research efforts. The interview will take 10 – 15 minutes to complete and participants will be compensated with a \$5 gift card as thanks for their time and participation.

(f) Repeat STI Interviews: Preliminary data analysis indicates that a subset of KIU participants tested positive for rectal STIs more than once during the study. We plan to continue refining the KIU program in future research, so we are interested in getting a better understanding of what factors are contributing to repeat STIs

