in this subset of participants. This information will allows us to add content to future iterations of the intervention to address these issues and hopefully reduce the occurrence of repeat STIs in this population. In order to gain this important information, we have created a brief interview script to collect qualitative data from 20 randomly selected participants from a pool of participants who tested positive for rectal STIs more than once during the study. We will conduct interviews by phone to learn about participants' experiences getting tested for and seeking treatment for rectal STIs, including their reactions to testing positive for a rectal STI, how it influenced their thinking and behavior, and their experiences related to seeking treatment (e.g., barriers to seeking treatment, doctors' reactions). We will record the interviews by putting the call on speakerphone mode and using a handheld digital recording device. Before beginning the interviews, the study team will describe the potential risks and benefits associated with participating in the interview, describe how we handle privacy and confidentiality, and ask participants for verbal consent to participate in the interview and to have it audio recorded. Participants will be reminded that all of the information they provide during the interview is confidential and that they can refuse to answer any questions that they do not feel comfortable answering. The study team will transcribe the audio and conduct qualitative data analyses in order to identify themes in responses. The information gained from the qualitative interviews will help to broaden our understanding of risk for repeat rectal STIs, including identifying factors that may be barriers to accessing treatment. This information has the potential to inform future development of HIV/STI prevention interventions for this population. The interview will take 10-15 minutes to complete and participants will be compensated with a \$10 gift card as thanks for their time and participation. Participants who are difficult to reach (defined as non-responsive to 3 contact attempts) will be offered a \$20 gift card as thanks for their time and participation. Participants who are recruited for these interviews come from a relatively small subset of participants who tested positive for rectal STIs more than once during the study, so we hope increasing the incentive for difficult to reach participants will help us reach our goal of 20 interviews. Increased incentives like this have been shown to increase participation among difficult to reach and non-responsive participants in other research studies without perceptions of coercion.

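### Incident NG/CT is not defined and men infected at baseline stay in the STI analysis, so infections that never cleared may be counted as new

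*Protocol*

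**What the plan says.** Protocol B.6 states the role of the endpoint: "Joint NG/CT incidence will serve as a biomedical endpoint for establishing intervention efficacy". B.11 and SAP C3 repeat it as the biomedical endpoint of Aim 2.

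Testing is described in the same way in several places. Protocol B.10(d), table row on STI incidence, says "All participants will be tested at baseline and 12 month follow-up" and adds: "Participants who test positive at baseline will also be tested at 3 month and 6 month follow-ups". The Procedures section of the protocol agrees: "Participants who test positive at baseline will be tested at 3 month and 6 month follow-up in addition to at the 12 month follow-up". C.2.e and SAP F.3.f match. The eligibility criteria (B.7, C.1.a, SAP A.4) do not exclude men with NG/CT at baseline.

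For the analysis, B.11 and SAP C3 specify a mixed model over all follow-up points, with a random intercept, the baseline value of the outcome as a covariate, and one group effect averaged over time. The analysis set is described as "Analysis of all available measurements among all participants regardless of dose".

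B.10(h) and SAP A.3 add that testing, results and treatment before the 12-month test are self-reported at the behavioural assessments. Neither B.11 nor SAP C3 says how those reports enter the endpoint. No section gives an at-risk set, a rule for when a later positive is incident, or a use for the 3- and 6-month results.

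**The concern.** The intervention cannot prevent an infection that was present before its content was delivered. If such an infection is still detectable later and enters the outcome, it adds an event unrelated to the intervention's preventive effect.

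The stated model leaves this open. It includes men infected at baseline, and only they have scheduled study tests at 3 and 6 months. A group effect averaged over time would therefore rest, at two of its three follow-up points, entirely on the men whose positives are hardest to classify. The missing-data assumption in B.11 does not help: no man negative at baseline has a scheduled 3- or 6-month test, so the model has no observations from which to learn his outcome there. The baseline covariate adjusts for baseline status, but it does not turn a persistent infection into a new one.

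Repeat positives do occur. B.10(f) reports that "a subset of KIU participants tested positive for rectal STIs more than once during the study". It does not say whether these were persistent or new infections. At stake are the effect estimate on a primary endpoint and the meaning of the word incidence in the trial's report.

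**Working it through.** **Inputs**
- 900 men at 1:1 (Protocol, Study Design) and 80% retention (B.12): 720 retained, 360 per arm. The SAP's 375 per arm would give 300.
- Baseline prevalence b = 10.2%, the only planning figure (B.2(c)). It is from urine alone; this trial adds rectal tests, so b = 20% is also shown, as an assumption.
- Control incidence 10% or 15% (B.12).
- q, the share of baseline positives still positive and counted later. The documents give no value; 10-30% is assumed.

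**The plan's own figure.** B.12 states power of 81/70/56% for reductions of 7/6/5 points from 10%, and 71/60/47% from 15%. I used a two-sided pooled test of two proportions at 0.05:

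power = Φ{[d − 1.96·√(2p̄(1−p̄)/n)] / √[(p₁(1−p₁)+p₂(1−p₂))/n]}

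- n = 360: 96.9/88.6/72.2% and 83.9/69.8/52.7%.
- n = 300: 93.7/82.3/64.3% and 76.8/61.9/45.7%.

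The stated figures do not reproduce as reductions. All six come within 2 points only if the difference is added to the control rate with 400 per arm, a number the documents do not give. That is a separate matter. The power changes below start from the recomputed 72.2% (10% against 5%, n = 360).

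**Where the follow-up tests come from** (every scheduled test done by retained men)
- Baseline positives: 720 × 0.102 = 73.4 men × 3 tests = 220.
- Baseline negatives: 646.6 men × 1 test = 647.
- Share: 220 / 867 = 25%. At b = 20%: 432 / 1008 = 43%.

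**Dilution if persistent infections are counted, equally in both arms.** Per arm, true events are 36 (control, 10% of 360) and 18 (KIU!, 5%), so the true ratio is 0.50. Baseline positives per arm are 73.4 / 2 = 36.7.
- q = 10% adds 3.7: (18 + 3.7) / (36 + 3.7) = 0.55.
- q = 30% adds 11: (18 + 11) / (36 + 11) = 0.62.

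Allowing for a man having both a persistent and a new infection, the counted rate is 1 − (1 − p)(1 − bq):

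| b | q | Observed ratio | Power, n = 360 |
|---|---|---|---|
| 10.2% | 10% | 0.55 | 66.6% |
| 10.2% | 25% | 0.60 | 59.2% |
| 20% | 10% | 0.59 | 61.8% |
| 20% | 25% | 0.67 | 49.7% |

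At b = 10.2%, the share of counted control-arm positives that are not new is 8% (q = 10%) or 19% (q = 25%).

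**Cost of excluding them.** The strictest option analyses only men negative on every baseline test: 360 × 0.898 = 323 per arm. Power becomes 95.2/85.0/67.6% (control 10%) and 79.8/65.1/48.5% (control 15%), a loss of about 2-5 points. This still beats counting everyone once q exceeds about 7-8% (control 10%) or 13-14% (control 15%).

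**The case against.** The strongest reply is that the plan never says a persistent infection counts as new. It calls the endpoint incidence throughout, and some text frames STI testing as a comparison of baseline with 12 months (Protocol, Procedures; SAP B.2). It also collects self-reported treatment, which could help separate old infections from new. This stands against any claim that persistent infections will be counted. It does not supply a rule: the analysis sections name neither a 12-month endpoint nor a use for the treatment reports, and a report of treatment does not document clearance.

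Treatment arrangements are also better than bare referral. Clinic staff are responsible for treating men tested at Chicago Department of Public Health clinics (B.10(h)), and study staff follow up with the others (C.2.e). This may keep persistence low, and at q = 10% the loss of power is modest.

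A reader might infer that the extra 3- and 6-month tests cause the problem. They do so only if each positive is entered as an outcome; used differently, a negative result between two positives helps to show that the later one is new. A reader might also take B.10(f) as evidence of untreated infection. Its phrase "identifying factors that may be barriers to accessing treatment" describes what planned interviews hope to learn, not something observed, and the section does not say that the repeat positives began at baseline.

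**Conclusion.** The point holds as a missing definition with a foreseeable consequence. Followed literally, the stated model keeps men infected at baseline, and nothing in the plan stops a persistent infection from being counted as incident.

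Under equal persistence of 10-30%, a true risk ratio of 0.50 would appear as about 0.55-0.62. These are crude ratios, not output from the planned covariate-adjusted model. They rest on an assumed q and on a prevalence from urine tests alone.

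The documents do not support the stronger statement that the effect will be diluted. That needs persistence to be equal in the arms. KIU! covers STI symptoms and regular testing (B.3), so it could change treatment seeking, and the bias could then go in either direction. That uncertainty is a further reason to fix the case definition before outcomes are compared. The change should be made, although its practical size cannot be known from the documents.

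**What to change.** In Protocol B.11 and SAP C3:

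1. Define the primary STI endpoint as a positive 12-month test for an organism (NG or CT) and site (urethral or rectal) at which the man was negative at baseline. The joint NG/CT event is at least one such positive.
2. Do not enter the 3- and 6-month results, which exist only for men positive at baseline, as outcomes in the group-effect model.
3. As a sensitivity analysis, also count a 12-month positive at an organism and site positive at baseline when a negative 3- or 6-month study test or self-reported treatment came in between. Keep men without that information in the denominator as non-events, so that the set is not selected on post-randomisation data.
4. Report the remaining positives separately as persistent or unresolved.
5. State how missing site results are handled, since SAP A.3 offers men living abroad rectal testing only where possible.

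This needs wording and a derivation by organism and site from tests already scheduled; no new testing is required. The price is that true reinfections at the same organism and site are left out of the primary endpoint. Even the stricter restriction to men negative on all baseline tests costs only about 2-5 points of power at 10.2% prevalence.
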